## **11.0 STUDY MANAGEMENT**

### **11.1 Institutional Review Board (IRB) Approval and Consent**

It is expected that the IRB will have the proper representation and function in accordance with federally mandated regulations. The IRB should approve the consent form and protocol.

In obtaining and documenting informed consent, the investigator should comply with the applicable regulatory requirement(s), and should adhere to Good Clinical Practice (GCP) and to ethical principles that have their origin in the Declaration of Helsinki.

Before recruitment and enrollment onto this study, the patient will be given a full explanation of the study and will be given the opportunity to review the consent form. Each consent form must include all the relevant elements currently required by the FDA Regulations and local or state regulations. Once this essential information has been provided to the patient and the investigator is assured that the patient understands the implications of participating in the study, the patient will be asked to give consent to participate in the study by signing an IRB approved consent form.

Prior to a patient's participation in the trial, the written informed consent form should be signed and personally dated by the patient and by the person who conducted the informed consent discussion.

### **11.2 Amendments**

The Principal Investigator will formally initiate all amendments to the protocol and/or informed consent. All amendments will be subject to the review and approval of the appropriate local, institutional, and governmental regulatory bodies, as well as by BMS.

### **11.3 Registration Procedures**

Patients may not begin protocol treatment prior to registration. All patient registrations will be registered centrally through the Clinical Research Office at Northwestern University before enrollment to study. Please contact the assigned Quality Assurance Monitor (QAM) or email the QA Department ([[contact]](mailto:[contact])) for questions regarding patient registration.

Prior to registration, eligibility criteria must be confirmed by the assigned QAM. The study coordinator will screen all subjects for potential registration via the web-based application NOTIS (Northwestern Oncology Trial Information System), which is available at: <https://notis.nubic.northwestern.edu>. Please note that a username and password is required to use this program, and will be provided during site activation prior to training on the NOTIS system. Training on eCRF completion will be provided at the time of site activation.

BEFORE a patient can be treated on study, please complete and submit the following items to confirm eligibility and receive an identification number:

- Patient's signed and dated informed consent form (upload to NOTIS and keep original hard copy in a secure location/study chart)
- Eligibility checklist (signed and dated by the treating physician – upload to NOTIS)
- Eligibility eCRF (complete in NOTIS)
- Copy of the pathology report (upload to NOTIS)

The QAM will review the registration, register the patient, assign a subject identification number, and send a confirmation of registration to study personnel. Registration will then be complete and the patient may begin study treatment.

#### **11.4 Data Management and Monitoring/Auditing**

This study will be conducted in compliance with the Data Safety Monitoring Plan (DSMP) of the Robert H. Lurie Comprehensive Cancer Center of Northwestern University (please refer to Appendices for additional information). The level of risk attributed to this study requires high monitoring, as outlined in the DSMP. The assigned QAM, with oversight from the Data Monitoring Committee, will monitor this study in accordance with the study phase and risk level.

This study will be conducted in compliance with the Data Safety Monitoring Plan (DSMP) of the Robert H. Lurie Comprehensive Cancer Center of Northwestern University (please refer to Appendices for additional information). The level of risk attributed to this study requires High Intensity Monitoring as outlined in the DSMP. The assigned QAM, with oversight from the Data Monitoring Committee, will monitor this study in accordance with the study phase and risk level.

Once a subject is confirmed and registered to the study, eCRFs should be submitted according to the detailed data submission guidelines (provided in a separate document).

#### **11.5 Adherence to the Protocol**

Except for an emergency situation in which proper care for the protection, safety, and well-being of the study patient requires alternative treatment, the study shall be conducted exactly as described in the approved protocol.

##### **11.5.1 Emergency Modifications**

Investigators may implement a deviation from, or a change of, the protocol to eliminate an immediate hazard(s) to trial subjects without prior IRB approval.

For any such emergency modification implemented, an IRB modification form must be completed within 5 business days of making the change, and the QAM must be notified within 24 hours of such change.

##### **11.5.2 Other Protocol Deviations**

All other deviations from the protocol must be reported to the assigned QAM using the appropriate form.

A protocol deviation is any unplanned variance from an IRB approved protocol that:

- Is generally noted or recognized after it occurs.
- Has no substantive effect on the risks to research participants.

- Has no substantive effect on the scientific integrity of the research plan or the value of the data collected.
- Did not result from willful or knowing misconduct on the part of the investigator(s).

A protocol deviation may be considered an instance of Promptly Reportable Non-Compliance (PRNC) if it:

- Has harmed or increased the risk of harm to one or more research participants.
- Has damaged the scientific integrity of the data collected for the study.
- Results from willful or knowing misconduct on the part of the investigator(s).
- Demonstrates serious or continuing noncompliance with federal regulations, State laws, or University policies.

#### **11.6 Investigator Obligations**

The Principal Investigator is responsible for the conduct of the clinical trial at the site in accordance with Title 21 of the Code of Federal Regulations and/or the Declaration of Helsinki. The PI is responsible for personally overseeing the treatment of all study patients. The PI must assure that all study site personnel, including sub-investigators and other study staff members, adhere to the study protocol and all FDA/GCP/NCI regulations and guidelines regarding clinical trials both during and after study completion.

The Principal Investigator at each institution or site will be responsible for assuring that all the required data will be collected, entered onto the appropriate eCRFs, and submitted within the study-specific timeframes. Periodically, monitoring visits may be conducted and the Principal Investigator will provide access to his/her original records to permit verification of proper entry of data. The study may also be subject to routine audits by the Audit Committee, as outlined in the DSMP.

#### **11.7 Publication Policy**

All potential publications and/or data for potential publications (e.g. manuscripts, articles, data, text, diagrams, abstracts, posters, charts, slides, pictures, or clinicaltrials.gov releases) must be approved in accordance with the policies and processes set forth in the Lurie Cancer Center DSMP. The assigned QAM will prepare a preliminary data summary (to be approved by the DMC) no later than 3 months after the study reaches its primary completion date (the date that the final subject is examined or receives an intervention for the purposes of final data collection for the primary endpoint). If the investigator's wish to obtain DMC-approved data prior to this point (or prior to the point dictated by study design), the PI must send a written request for data to the QAM which includes justification. If the request is approved, data will be provided no later than 4 weeks after this request approval. The data will be presented to the DMC at their next available meeting, and a final, DMC-approved dataset will be released along with any DMC decisions regarding publication. The investigators are expected to use only DMC-approved data in future publications. The investigators should submit a copy of the manuscript to the biostatistician to confirm that the DMC-approved data are used appropriately. Once the biostatistician gives final approval, the manuscript may be submitted to external publishers.

NU shall provide BMS with a copy of each Publication at the earliest practicable time, but in any event not less than thirty (30) days prior to its submission to a journal, publisher or meeting or fifteen (15) days prior to any public disclosure of

any manuscript or other public disclosure (e.g., presentations). To the extent applicable, BMS personnel shall be acknowledged (including authorship where applicable) in accordance with customary scientific practice.

## **APPENDICES**

### **Appendix A Common Terminology Criteria for Adverse Events V4.0.3 (CTCAE)**

The descriptions and grading scales found in the revised NCI Common Terminology Criteria for Adverse Events (CTCAE) version 4.0.3 will be utilized for adverse event reporting. (<http://ctep.cancer.gov/reporting/ctc.html>)

## Appendix B – Contraception Requirements

Investigators shall counsel WOCBP and male subjects who are sexually active with WOCBP on the importance of pregnancy prevention and the implications of an unexpected pregnancy. Investigators shall advise WOCBP and male subjects who are sexually active with WOCBP on the use of highly effective methods of contraception. Highly effective methods of contraception have a failure rate of < 1% per year when used consistently and correctly.

At a minimum, subjects must agree to the use of two methods of contraception, with one method being highly effective and the other method being either highly effective or less effective as listed below:

### HIGHLY EFFECTIVE METHODS OF CONTRACEPTION

- a) Male condoms with spermicide
- b) Hormonal methods of contraception including combined oral contraceptive pills, vaginal ring, injectables, implants, and intrauterine devices (IUDs) such as Mirena® by WOCBP subject or male subject's WOCBP partner. Female partners of male subjects participating in the study may use hormone based contraceptives as one of the acceptable methods of contraception since they will not be receiving study drug.
- c) Nonhormonal IUDs, such as ParaGard®
- d) Tubal ligation
- e) Vasectomy.
- f) Complete Abstinence\*

\*Complete abstinence is defined as complete avoidance of heterosexual intercourse and is an acceptable form of contraception for all study drugs. Subjects who choose complete abstinence are not required to use a second method of contraception, but female subjects must continue to have pregnancy tests. Acceptable alternate methods of highly effective contraception must be discussed in the event that the subject chooses to forego complete abstinence.

### LESS EFFECTIVE METHODS OF CONTRACEPTION

- a) Diaphragm with spermicide
- b) Cervical cap with spermicide
- c) Vaginal sponge
- d) Male Condom without spermicide\*
- e) Progestin only pills by WOCBP subject or male subject's WOCBP partner
- f) Female Condom\*

\*A male and female condom must not be used together

Azoospermic males and WOCBP who are continuously not heterosexually active are exempt from contraceptive requirements. However they must still undergo pregnancy testing as described in this sections.

**Appendix C**

**ECOG Performance Status**

[figure not shown]
Grade	Description
0	Normal activity. Fully active, able to carry on all pre-disease performance without restriction.
1	Symptoms, but ambulatory. Restricted in physically strenuous activity, but ambulatory and able to carry out work of a light or sedentary nature (e.g., light housework, office work).
2	In bed <50% of the time. Ambulatory and capable of all self-care, but unable to carry out any work activities. Up and about more than 50% of waking hours.
3	In bed >50% of the time. Capable of only limited self-care, confined to bed or chair more than 50% of waking hours.
4	100% bedridden. Completely disabled. Cannot carry on any self-care. Totally confined to bed or chair.
5	Dead.

* As published in Am. J. Clin. Oncol.: Oken, M.M., Creech, R.H., Tormey, D.C., Horton, J., Davis, T.E., McFadden, E.T., Carbone, P.P.: Toxicity And Response Criteria Of The Eastern Cooperative Oncology Group. Am J Clin Oncol 5:649-655, 1982. The Eastern Cooperative Oncology Group, Robert Comis M.D., Group Chair.
	

## Appendix D – Adverse Events Algorithm

Recommended management algorithms for suspected nivolumab related endocrinopathy, gastrointestinal toxicity, hepatotoxicity, neurologic toxicity, pulmonary toxicity, renal toxicity and skin toxicity

### Endocrinopathy Management Algorithm

[figure not shown]
Rule out non-inflammatory causes. If non-inflammatory cause, treat accordingly and continue I-O therapy. Consider visual field testing, endocrinology consultation, and imaging.

Patients on IV steroids may be switched to an equivalent dose of oral corticosteroids (e.g. prednisone) at start of tapering or earlier, once sustained clinical improvement is observed. Lower bioavailability of oral corticosteroids should be taken into account when switching to the equivalent dose of oral corticosteroids.

## GI Adverse Event Management Algorithm

[figure not shown]
Rule out non-inflammatory causes. If non-inflammatory cause is identified, treat accordingly and continue I-O therapy. Opiates/narcotics may mask symptoms of perforation. Infliximab should not be used in cases of perforation or sepsis.

Patients on IV steroids may be switched to an equivalent dose of oral corticosteroids (e.g. prednisone) at start of tapering or earlier, once sustained clinical improvement is observed. Lower bioavailability of oral corticosteroids should be taken into account when switching to the equivalent dose of oral corticosteroids.

## Hepatic Adverse Event Management Algorithm

Rule out non-inflammatory causes. If non-inflammatory cause, treat accordingly and continue I-O therapy. Consider imaging for obstruction.

Patients on IV steroids may be switched to an equivalent dose of oral corticosteroids (e.g. prednisone) at start of tapering or earlier, once sustained clinical improvement is observed. Lower bioavailability of oral corticosteroids should be taken into account when switching to the equivalent dose of oral corticosteroids.

\*I-O therapy may be delayed rather than discontinued if AST/ALT ≤ 8 x ULN and T.bili ≤ 5 x ULN.

\*\*The recommended starting dose for grade 4 hepatitis is 2 mg/kg/day methylprednisolone IV.

e

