### **4.1 Treatment Administration**

Treatment will be administered on an outpatient basis. Reported adverse events and potential risks are described below. No investigational or commercial agents or therapies other than those described below may be administered with the intent to treat the patient's malignancy.

Nivolumab will be administered at a dose of 240mg as an intravenous infusion over 30 minutes every 2 weeks until disease progression, unacceptable toxicity, or withdrawal of consent.

There will be no dose escalations or reductions of nivolumab allowed. Subjects may be dosed no less than 12 days from the previous dose. There are no pre-medications recommended for nivolumab on the first cycle. If an acute infusion reaction is noted, subjects should be managed according to Section 4.2.4.

Nivolumab is to be administered as a 30-minute IV infusion (a window of +/- 5 minutes is allowed), using a volumetric pump with a 0.2/1.2 micron in-line filter at the protocol-specified dose. The drug can be diluted with 0.9% normal saline for delivery but the total drug concentration of the solution cannot be below 1 mg/mL. It is not to be administered as an IV push or bolus injection. At the end of the infusion, flush the line with a sufficient quantity of normal saline.

Subjects will be monitored continuously for AEs while on study. Treatment modifications (e.g., dose delay or discontinuation) will be based on specific laboratory and adverse event criteria.

Early recognition and management may mitigate severe toxicity. Evaluation and Management Guidelines were developed to assist investigators and can be found in the Investigator Brochure:

- Suspected Pulmonary Toxicity
- Diarrhea and Colitis
- Suspected Hepatotoxicity (including asymptomatic liver function tests [LFT] elevations)
- Suspected Endocrinopathy
- Nephrotoxicity

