#### **4.2 Dosing delays, support care, and discontinuation of therapy**

There will be no dose modifications allowed for management of toxicities.

Nivolumab administration should be delayed for the following until resolution to  $\leq$  Grade 1:

- Any Grade  $\geq 2$  non-skin, drug-related adverse event, with the following exceptions:
  - Grade 2 drug-related fatigue or laboratory abnormalities do not require a treatment delay
  - Any Grade 3 skin, drug-related adverse event
  - Any Grade 3 drug-related laboratory abnormality, with the following exceptions for lymphopenia, leukopenia, AST, ALT, or total bilirubin:
    - Grade 3 lymphopenia or leukopenia does not require dose delay
    - If a subject has a baseline AST, ALT or total bilirubin that is within normal limits, delay dosing for drug-related Grade  $\geq 2$  toxicity
    - If a subject has baseline AST, ALT, or total bilirubin within the Grade 1 toxicity range, delay dosing for drug-related Grade  $\geq 3$  toxicity
- Any adverse event, laboratory abnormality, or intercurrent illness which, in the judgment of the investigator, warrants delaying the dose of study medication.

Immuno-oncology (I-O) agents are associated with AEs that can differ in severity and duration than AEs caused by other therapeutic classes. Nivolumab is considered an immuno-oncology agent in this protocol. Early recognition and management of AEs associated with immuno oncology agents may mitigate severe toxicity. Management Algorithms have been developed to assist investigators in assessing and managing the following groups of AEs:

- Gastrointestinal
- Renal
- Pulmonary
- Hepatic
- Endocrinopathy
- Skin
- Neurological

The above algorithms are found in the nivolumab Investigator Brochure and appendix D of this protocol.

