##### **4.2.1 Treatment discontinuation criteria**

Nivolumab treatment should be permanently discontinued for the following:

- Any Grade 2 drug-related uveitis, eye pain or blurred vision that does not respond to topical therapy and does not improve to Grade 1 severity
- Any Grade 3 non-skin, drug-related adverse event lasting > 7 days
- Grade 3 drug-related uveitis, pneumonitis, bronchospasm, hypersensitivity reaction, or infusion reaction of any duration requires discontinuation
- Grade 3 drug-related laboratory abnormalities do not require treatment discontinuation except:
  - Grade 3 drug-related thrombocytopenia > 7 days or associated with bleeding requires discontinuation
  - Any drug-related liver function test (LFT) abnormality that meets the following criteria requires discontinuation:
    - AST or ALT > 5-10x ULN for > 2 weeks
    - AST or ALT > 10x ULN
    - Total bilirubin > 5x ULN
    - Concurrent AST or ALT > 3x ULN and total bilirubin > 2x ULN
- Any Grade 4 drug-related adverse event or laboratory abnormality, except for the following events:
  - Grade 4 neutropenia  $\leq$  7 days does not require discontinuation
  - Grade 4 lymphopenia or leukopenia does not require discontinuation
  - Isolated Grade 4 electrolyte imbalances/abnormalities that are not associated with clinical sequelae and are corrected with supplementation/appropriate management within 72 hours of their onset do not require discontinuation
  - Isolated Grade 4 amylase or lipase abnormalities not associated with symptoms or clinical manifestations of pancreatitis. The PI and Data Monitoring Committee (DMC) should be notified of Grade 4 amylase or lipase abnormalities (please do so by sending an email to [[contact]](mailto:[contact]))
- Any dosing interruption lasting > 6 weeks with the following exceptions:
  - Dosing interruptions to manage drug-related adverse events, such as prolonged steroid tapers, are allowed. Prior to re-initiating treatment in a subject with a dosing interruption lasting > 6 weeks, the PI and DMC should be consulted (by emailing [[contact]](mailto:[contact])). Tumor assessments should continue as per protocol even if dosing is interrupted.

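### The hepatic footnote in Appendix D permits a hold where section 4.2.1 requires permanent discontinuation, and no visible text says which rule governs

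*Combined protocol and SAP*

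**What the plan says.** Section 4.2.1 lists the reasons for stopping nivolumab permanently. For liver tests it says: "Any drug-related liver function test (LFT) abnormality that meets the following criteria requires discontinuation". Four criteria follow:

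- "AST or ALT > 5-10x ULN for > 2 weeks"
- AST or ALT above 10x ULN
- total bilirubin above 5x ULN
- "Concurrent AST or ALT > 3x ULN and total bilirubin > 2x ULN"

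The last of these has no duration condition and no exception.

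The footnote to the hepatic algorithm in Appendix D addresses the same decision: "I-O therapy may be delayed rather than discontinued if AST/ALT ≤ 8 x ULN and T.bili ≤ 5 x ULN". Its visible text makes no exception for combined elevation.

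On the standing of the two texts, section 4.1 says: "Treatment modifications (e.g., dose delay or discontinuation) will be based on specific laboratory and adverse event criteria". Section 4.2 says: "Management Algorithms have been developed to assist investigators in assessing and managing the following groups of AEs", and then: "The above algorithms are found in the nivolumab Investigator Brochure and appendix D of this protocol". The opening line of Appendix D describes the algorithms as recommended. Section 11.5 requires the study to be run as the approved protocol describes, emergencies aside.

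**The concern.** One part of the protocol orders a permanent stop, and another part offers a hold for the same laboratory values. The values matter clinically: a transaminase rise together with a bilirubin rise has its own line in 4.2.1, at lower limits than either test alone.

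At stake is re-exposure. A site that follows the footnote could hold the drug, see recovery, and resume in a patient whom 4.2.1 says must not resume. Section 4.2 allows no dose modification, so the restart would be at the full 240 mg. Section 3.1.6 admits patients with liver metastases at AST/ALT up to 5x ULN, so some could enter already above the 3x limb of the combined criterion. Section 3.0 names four institutions, and they could resolve the mismatch differently.

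**Working it through.** No sample size, power or alpha figure is involved. The check compares two sets of inequalities and then asks what the text says about precedence.

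**Notation.** A is the larger of AST and ALT, and B is total bilirubin, both in multiples of ULN. The footnote applies when A ≤ 8 and B ≤ 5. Each 4.2.1 criterion, if drug-related, is compared with that range:

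| 4.2.1 liver criterion | Overlap with the footnote range | Reading |
|---|---|---|
| A > 10 | none, since 10 > 8 | consistent |
| B > 5 | none | consistent |
| A > 5 to 10 for more than 2 weeks | 5 < A ≤ 8, B ≤ 5, only after 2 weeks | reconcilable: hold first, stop once 2 weeks have passed |
| A > 3 and B > 2, any duration | 3 < A ≤ 8 and 2 < B ≤ 5 | direct conflict |

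**Example.** Take A = 4 and B = 3. Footnote: 4 ≤ 8 and 3 ≤ 5, so delay is permitted. Section 4.2.1: 4 > 3 and 3 > 2, so discontinuation is required.

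**Ceiling of the footnote.** Take A = 8 and B = 5. Since 8 > 3 and 5 > 2, the most extreme case in which the footnote permits delay already meets the stop rule. To agree with 4.2.1, the footnote's bilirubin limit would have to be 2x rather than 5x whenever A exceeds 3.

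**Effect of the unseen box.** Suppose the flowchart box sets lower entry limits a on A and b on B, with a < 8 and b < 5 (otherwise the footnote would never apply). The overlap becomes max(3, a) < A ≤ 8 with max(2, b) < B ≤ 5. This may be smaller, but it is not empty. Only an explicit exception for combined elevation, or wording that defers to 4.2.1, would remove the conflict.

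**Precedence.** Section 4.2.1 uses *requires*. The footnote uses *may*, the opening line of Appendix D uses *Recommended*, and 4.2 says the algorithms *assist*. A site that discontinues satisfies both texts, while a site that delays breaches 4.2.1. The natural inference is that 4.2.1 governs. Against that, 4.2 places the algorithms inside the protocol, 11.5 gives no order among its parts, and no visible sentence ranks them.

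**Path to restart.** Under 4.2, dosing resumes only after resolution to Grade 1 or less. Section 4.2.1 adds: "Prior to re-initiating treatment in a subject with a dosing interruption lasting > 6 weeks, the PI and DMC should be consulted". Dosing is every 2 weeks, so 6 / 2 = 3 dosing intervals can pass before that step is triggered. A patient who recovers sooner can restart without it.

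**The case against.** The strongest reply is that there is no real contradiction: a mandatory rule sits beside a permissive aid, and both can be obeyed by stopping. Section 4.1 ties delay and discontinuation to specific criteria. Section 4.2.1 writes out its own exceptions, and Appendix D is not among them. This stands as the better reading of the text. It does not settle the matter, because the page written for managing liver toxicity expressly offers the opposite choice, and a treating clinician has to infer that the offer does not apply.

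The second reply is that a footnote is being read without its figure, and the Investigator Brochure, which also holds the algorithms, is not available here. This stands as a limit. A reader might infer that the plan contains no ranking anywhere; the documents support only the statement that none is visible.

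The third reply concerns harm. A reader might infer that restart would go unchecked. It would not:

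- Section 4.2.1 also requires a permanent stop when the investigator judges that continued dosing carries substantial clinical risk.
- The section 5.0 schedule has a chemistry panel at every dosing visit.
- Section 8.2 provides review before each dose and team conferences at least monthly.

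These reduce the risk. None of them states which rule governs.

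A reader might also count the 2-week transaminase criterion as a second direct conflict. It is only an ambiguity, because holding and then stopping at 2 weeks satisfies both texts.

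**Conclusion.** The point holds as an inconsistency between two stated safety rules. One of the four liver criteria in 4.2.1 conflicts directly with the footnote, at AST/ALT above 3x to 8x with bilirubin above 2x to 5x ULN, when the abnormality is drug-related. The lower end of that range rests on the visible wording and could move once the flowchart is seen. The upper corner stays in conflict unless the flowchart carries an explicit exception or defers to 4.2.1.

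The exposure is limited to patients who recover to Grade 1 or less within 6 weeks at a site that relies on the footnote despite 4.2.1. The documents give no frequency for combined elevation, so no number or share of patients can be stated. A reader might look for an effect on the trial's conclusions. There is none: the Simon two-stage rules, the error rates and the response analysis do not depend on this text. The correction should be made because it concerns a permanent-stop criterion. Confidence is medium, because the flowchart is not shown.

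**What to change.** Add to section 4.2, and repeat in the hepatic footnote, that the permanent-discontinuation criteria in 4.2.1 govern over Appendix D. Add also that the delay option applies only when no drug-related 4.2.1 liver criterion is met: not with AST or ALT above 3x ULN together with bilirubin above 2x ULN, and not once AST or ALT above 5x ULN has lasted more than 2 weeks. When making the change, check the flowchart box that carries the asterisk so that its wording agrees.

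The cost is two sentences in two places, with no change to visits, sample size or analysis. Sites lose the footnote's delay option in that range, but 4.2.1 already rules it out.
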